This study will consist of electromyography (surface and intramuscular), peripheral nerve stimulation, and transcranial magnetic stimulation, electrical stimulation, of the hand, arm, leg, and foot representation of the primary motor cortex, as well as MRI scans of the brain. We will examine the physiological measurements of upper and lower extremity muscles (such as in the first dorsal interosseous (FDI), biceps brachii (BIC), anterior deltoid (AD), tibialis anterior (TA), hamstring (HAMS) and quadriceps (QUAD)). This study may occur at the Miami Project to cure Paralysis at the University of Miami. We will include subjects between the ages of 18 and 85, both healthy controls and individuals with chronic spinal cord injuries that occurred at least 6 months prior to recruitment. Both healthy controls and those with spinal cord injuries will be able to perform small hand and arm movements and small leg and foot movements. The primary outcome measures of this study are muscle responses to stimulation with magnetic pulses using TMS and electrical stimulation of a peripheral nerve in the arm or leg. We propose to enhance the recovery of motor function by using new protocols of high frequency non-invasive repetitive TMS (rTMS) and motor training. Repetitive TMS will be used during hand, arm, leg and foot movements in a task-dependent manner to induce cortical plasticity and enhance voluntary output of the muscles associated with those movements. Second, rTMS will be applied in a task-dependent manner during a visuo-motor training task that also involves movements of the hands, arms, legs or feet.

Phase 1

Aim 1. Neural Control of Movements in SCI and Control Subjects

We will use TMS, CMEPS, and peripheral nerve stimulation to test the hypotheses that 'precision grip and wrist movements will be associated with reduced motor cortical (as measured by intracortical inhibition) and spinal inputs (as measured by F-wave persistence and amplitude) to hand and wrist motoneurons after cervical SCI compared to controls'. Subjects will be instructed to perform a precision grip (between index and thumb) and simultaneously wrist flexion or extension movements. Measurements of cortical and motoneuronal excitability will be acquired during movement.

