Motor function- We will use range of motion (ROM), JTT, Pinch force, Chedoke arm and Hand inventory, and sensory function of the upper and lower extremities using the American Spinal Injury Association (ASIA) sensory scores and Electrical Perceptual Threshold (EPT). These functional and sensory tests are described in detail in Aim 2a.

Plan for multiple rTMS sessions using Brainsight for MRI co-registration: to ensure that the same area of the motor cortex is stimulated during multiple rTMS sessions we will use the Brainsight co-registration system. We will use an MRI scanner located at the University of Miami Applebaum MRI center or at the Miami VA Medical center. Individuals will be asked to participate in the scan session at their convenience as soon as they are enrolled in Aim 1 of this proposal. Individuals who only participate in Aim 2 of the study will be asked to have the MRI session after they have signed the consent form.

Plan for assessment of long-term effects of rTMS: Physiological and behavioral measurements will be acquired before and after sessions 1,5, and 10.

Phase 3- Follow up

Follow up measurements will be taken after 1, 2, and 3 months after Phase 3 testing to measure any sustained improvements in hand function. This assessment will be completed in a single session. These assessments will be the same as in Phase 1-3 of this research study. Each session will last about 1 hour.

Physiological measurements- We will examine MEPs, SICI, IHI, and F-waves (see procedures in Aim1). Precision Grip motor performance: we will examine Force onset, rate, area and total force duration (see procedures in Aim 2a.) Hand motor function: we will examine JTT, Pinch force, Chedoke Arm and Hand inventory, and sensory function of the hand using the American Spinal Injury Association (ASIA) sensory scores (see procedures in Aim 2a).

Assessment of quality of life and functional independence after SCI- the following measurements will be conducted before and after training sessions in Aim 2B, and at the follow up visits 1,2, and 3 months after training.

- (a) Self-care subscale of the spinal cord independence measure- Version III (SCIM; itzkovich et al., 2007)
- (b) The Capabilities of upper Extremities (CUE; Marino et al., 1998)

Demographics will be collected in all subjects. This will include variables such as age, gender, race, height, weight, and veteran status. For individuals with SCI, we will also collect level of injury and date of injury.

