Target population:

Male and female veterans with spinal cord injury at least 1 year after injury was sustained. We also plan to enroll control subjects who do not have any history of spinal cord injury.

Inclusion/Exclusion Criteria :

Participants who are unimpaired healthy controls:

- (1) Male and females between ages 18-85 years
- (2) Right handed
- (3) Able to complete precision grips with both hands

- (4) Able to complete full wrist flexion-extension bilaterally
- (5) Able to walk unassisted
- (6) Able to complete full ankle flexion-extension bilaterally

Participants who have had a spinal cord injury:

- (1) Male and females between ages 18-85 years
- (2) Chronic SCI (\geq 6 months of injury)
- (3) Spinal Cord injury at or above L5
- (4) The ability to produce a visible precision grip force with one hand
- (5) Individuals who have the ability to pick up a small object (large paperclip) from a table independently
- (6) Able to perform some small wrist flexion and extension (measured by a goniometer)
- (7) The ability to perform a small visible contraction with dorsiflexor and hip flexor muscles
- (8) No subjects will be excluded based on their race, religion, ethnicity, gender or HIV status.

Exclusion criteria for enrollment For SCI and Healthy Control Subjects (for stimulation):

- (1) Uncontrolled medical problems including pulmonary, cardiovascular or orthopedic disease
- (2) Any debilitating disease prior to the SCI that caused exercise intolerance
- (3) Premorbid, ongoing major depression or psychosis, altered cognitive status
- (4) History of head injury or stroke
- (5) Metal plate in skull
- (6) History of seizures
- (7) Receiving drugs acting primarily on the central nervous system, which lower the seizure threshold (see appendix 2)
- (8) Pregnant females
- (9) Ongoing cord compression or a syrinx in the spinal cord or who suffer from a spinal cord disease such as spinal stenosis, spina bifida, MS, or herniated cervical disk
- (10) Individuals with scalp shrapnel, cochlear implants, or aneurysm clips.

Qualified subjects can participate in up to 190 visits for this study. Visit range from 1-3 hours in length.

Start date: 11/2015.

Completion Date: 12/2019

E. Risks

This is a minimal risk proposal.

TMS procedures:

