Screening Interview: Identifiable information collected during either the screening interview will be destroyed if the potential subject does not qualify. If the subject does qualify and ultimately enrolls into this research, all information collected will become part of their research record. All security precautions that are reflected in this protocol will apply.

Data Collection and Storage: Research records will be retained in accordance with the Veterans Health Administration (VHA) Records Control Schedule. The Federal Privacy Act protects the confidentiality of medical records. Electronically-stored medical information collected from study participants will be kept on a VA server. Electronic data recorded during experimental sessions will be kept on fully-secured computers (password protected) on a VA server. Unique subject identifiers (i.e., a code accessible only to the PI and AI) will be used to label all electronic data files.

F. Sample Size

Up to 500 participants (250 SCI, and 250 control subjects) will be recruited to participate in this study at the VAMHS and at the University of Miami. Based on our previous protocols testing spinal cord injured subjects and healthy control subjects, we have added a 25% attrition rate to the number of subjects we plan to enroll in the study.

All participants will be between 18 and 85 years of age. We plan to recruit both veterans and non-veterans.

G. Data analysis is consistent with the study objective

Aim 1: Repeated-measures ANOVA and Tukey post hoc test will be used to assess the effect of TASK (rest, precision grip/wrist flexion, and precision grip/wrist extension) and GROUP (SCI, controls) on physiological measurements.

Aim 2a: Repeated measures ANOVA and Tukey post hoc test will be used to determine the effect of TIME (0,10, 30, 60 min after a single rTMS session), STIMULATION (rTMS, sham rTMS over control brain area) on physiological and behavioral measurements.

Aim 2b: repeated measures of ANOVA and Tukey post hoc analysis will be used to determine effects of GROUP (training + rTMS, training + sham rTMS), TIME (sessions number 1,5,10 and follow up 1,2, and 3 months) on physiological outcomes and motor performance.

H. Privacy and Confidentiality:

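### The Aim 1 comparison of SCI participants with controls is not randomised and does not adjust for age or sex, which are already collected, so the GROUP main effect is open to avoidable confounding; handedness and tested side also need a rule.

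*Combined protocol and SAP*

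**What the plan says.** Section G, Aim 1: "Repeated-measures ANOVA and Tukey post hoc test will be used to assess the effect of TASK" (rest, grip with wrist flexion, grip with wrist extension) "and GROUP (SCI, controls) on physiological measurements". No covariate is listed.

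Section C, Phase 1: the Aim 1 hypothesis is a between-group statement. It concerns intracortical inhibition and F-wave persistence and amplitude during the movements, as inputs "to hand and wrist motoneurons after cervical SCI compared to controls".

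Inclusion/Exclusion Criteria: the first item for both groups is "Male and females between ages 18-85 years". Section F repeats the range: "All participants will be between 18 and 85 years of age". No section describes matching, stratification, or an adjusted or sensitivity analysis for age or sex.

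Section C, demographics paragraph, for all subjects: "This will include variables such as age, gender, race, height, weight, and veteran status". Handedness is not named, but the wording leaves the list open.

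Handedness: item "2) Right handed" stands in the control criteria only. None of the eight SCI items mentions it. Controls must grip with both hands, whereas the SCI list asks for "The ability to produce a visible precision grip force with one hand". The Phase 1 motor task uses one hand, and the TMS measurements target the left or the right muscle. Neither text says how the side is chosen or how it relates to dominance.

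**The concern.** Aim 1 attributes a difference between two separately recruited samples to spinal cord injury. If the samples also differ in age or sex, and these are related to intracortical inhibition or F-waves, the unadjusted GROUP effect mixes the two sources. More recruitment does not help: the bias stays the same while the standard error shrinks, so a spurious difference becomes more likely to reach significance.

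The text gives reason to expect some imbalance. The target population is described as veterans with SCI, controls only as people without such a history, and Section F opens recruitment to non-veterans. Controls must also walk unassisted and complete full wrist and ankle movement on both sides. Nothing aligns the two samples on age or sex.

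Tested side is a related gap. An SCI participant who qualifies with one hand may have the side decided by residual function. A control is always right handed and can use either hand. The mix of dominant and non-dominant hands can therefore differ between groups.

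**Working it through.** **The plan's own figure.** There is none to reproduce on this point. The only sample size is up to 500 for the whole study (250 SCI, 250 controls) with a 25% attrition allowance. No alpha, power, effect size, SD or Aim 1 number is given.

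**Which effects are exposed.** Suppose age adds the same amount to a person's outcome in every task.
- TASK main effect: a contrast within persons, so the age term cancels.
- GROUP x TASK: a difference between groups in within-person contrasts, so the age term cancels again. It does not cancel if the age effect differs by task.
- GROUP main effect: a difference between groups in person means, so the age term stays.

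The same reasoning holds for sex.

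**Size for GROUP, on assumed inputs.** Let d be the gap in mean age in age SDs, r the within-group correlation of age with the outcome, and n the number per group.
- Bias in outcome SDs: b = r x d. With d = 0.25 to 0.75 and r = 0.2 to 0.4, b runs from 0.2 x 0.25 = 0.05 to 0.4 x 0.75 = 0.30.
- Rejection rate with no true GROUP effect, two-sided 5%: Phi(L - 1.96) + Phi(-L - 1.96), where L = b x sqrt(n/2).
- Worked case: b = 0.30 and n = 50 give L = 0.30 x 5 = 1.50, hence Phi(-0.46) + Phi(-3.46) = 0.323.

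| n per group | b = 0.05 | b = 0.15 | b = 0.30 |
|---|---|---|---|
| 20 | 5.3% | 7.6% | 15.8% |
| 50 | 5.7% | 11.7% | 32.3% |
| 188 | 7.7% | 30.7% | 82.9% |
| 250 | 8.6% | 38.9% | 91.8% |

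The 188 is 250 x 0.75 = 187.5, rounded up. With a weaker correlation, r = 0.1 and d = 0.25, b is 0.025 and the rate is 5.7% at 188 and 5.9% at 250.

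**Does adjustment work?** A simulation of 2,000 runs per setting fitted the group contrast with and without age and sex as covariates:

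| n per group | r | d | Unadjusted | Adjusted |
|---|---|---|---|---|
| 188 | 0.2 | 0.5 | 17.2% | 6.0% |
| 188 | 0.3 | 0.5 | 31.8% | 5.6% |
| 188 | 0.3 | 0.75 | 58.0% | 5.2% |
| 50 | 0.3 | 0.5 | 13.0% | 5.6% |

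Mean bias after adjustment was about zero in every row. Sex was unbalanced in these runs (80% against 50%) but had no effect on the outcome, so they show removal of age bias only. No size has been worked out for sex or for tested side.

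**Handedness.** A covariate for tested side, dominant or not, can be estimated because it can vary within both groups. A covariate for left-handedness cannot be separated from GROUP in the same way, since no control is left handed. Restricting to right-handed participants avoids that problem.

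**The case against.** **The magnitude is assumed.** This stands. No age gap or correlation is in the documents. At the low end of the range the false-positive rate is close to nominal at any plausible n.

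**250 per group is not an Aim 1 sample size.** This also stands. It is the ceiling for the whole study and includes the attrition allowance. The Brainsight/MRI paragraph refers to people who take part only in Aim 2. A reader might infer from the bottom row of the table that Aim 1 carries a false-positive rate of 39% or 92%; the documents support no single figure.

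**Not all of Aim 1 is exposed.** Correct. A reader might infer that every Aim 1 result is confounded. TASK is not, and GROUP x TASK is only if age or sex changes the task response. Individual calibration, with test stimuli at 50% of the maximal MEP and the SICI conditioning stimulus at 70% of AMT, may also narrow differences between persons. It does not remove them, and no normalisation of the F-wave response is described.

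**Handedness may already be recorded.** Possibly. The demographics list is open, and Section H refers to screening forms that are not in the documents. What can be said is that handedness is not named as collected in SCI participants, not that it is missing.

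**Matching is costly and late.** Fair. The pages are dated 03/01/19 and completion is given as 12/2019. Matching would change recruitment, and the fix does not depend on it.

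None of this answers the central point: the stated model leaves out age and sex, which the study already records.

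**Conclusion.** The point holds for the GROUP main effect, and for GROUP x TASK under the condition given. The contrast is not randomised, the stated model has no covariates, and age and gender are available for everyone. That much rests on the text alone.

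The size is not known. The range of about 6% to 32% at 50 per group, and about 9% to 92% at the 250 ceiling, rests on an assumed bias of 0.05 to 0.30 SD, no true GROUP effect and a two-sided 5% test. It covers age only. It shows what is possible, not what has happened: the documents do not show that the groups differ in age, sex or dominance, or that any GROUP finding would be false.

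The change should be made, because it protects the stated Aim 1 hypothesis and the main part needs no new data.

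**What to change.** 1. In Section G, Aim 1, add age and sex as covariates, each with its interaction with TASK. The protocol records gender, so state which variable will be used. Cost: analysis wording only.
2. Record handedness in SCI participants if it is not already on the screening form. Cost: one question, asked retrospectively where needed.
3. State how the tested hand is chosen, record it, and include tested side (dominant or not) in the model. Cost: a sentence and one data field.
4. Add a sensitivity analysis restricted to right-handed participants, since the covariate in item 3 cannot separate left-handedness from GROUP. Cost: some loss of SCI participants in that analysis.
5. Optional: frequency-match any controls still to be recruited to the SCI sample by sex and age band. This is a recruitment change, and the fix stands without it.

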During these motor tasks we will examine: (A) TMS measurements and (B) motoneuronal excitability in the first dorsal interosseous, and flexor and extensor carpis radialis muscles. TMS and peripheral nerve stimulation pulses will be delivered when subjects reach a certain degree of wrist flexion or extension and a certain percentage of MVC in the precision grip. Stimulation will be triggered if both goals are reached. This window in both directions will be modified for individuals who showed more difficulties in performing the movement in either direction.

(A) TMS measurements- Transcranial magnetic stimuli will be delivered from a stimulator through a figure-eight coil. TMS will be delivered to the optimal scalp position for activation of the left or right first dorsal interosseous, and flexor and extensor carpis radialis muscles. The TMS coil will be held to the head of the subject with a custom coil holder while the head is firmly secured to a headrest by straps to limit head movements. TMS measurements during precision grip and wrist movements will include the following:

MEPs – Resting and active motor thresholds (RMT and AMT) will be tested in each of the muscles. For this testing, TMS intensity will be adjusted to produce an MEP of 50% of the maximal MEP on each muscle tested. 30 MEPs will be average in each condition. Cervicomedullary Motor Evoked Potentials (CMEPs): Supramaximal electrical stimulation will be administered posterior to the mastoid process to elicit motor evoked potentials to upper and lower limb muscles.

Short-interval intracortical inhibition (SICI) – A conditioning stimulus (CS) will be set at an intensity of 70% of AMT. The test stimulus (TS) will be adjusted to produce an MEP of 50% of MEP-max. Test stimuli will be delivered 2.5 ms after CS. 25 TS and CS will be averaged in each condition.

Interhemispheric inhibition (IHI) – A supra-threshold CS will be set at an intensity above the RMT and given 10-50 ms before a TS delivered to the contralateral motor cortex. The coils will be positioned at the optimal location for activating the muscle tested and attached to coil holders.

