(B). Motoneuronal excitability (reflected by F-wave persistence and amplitude): F-waves will be tested by using supra-maximum stimulus intensity (120% of the maximal motor response) to the ulnar nerve at the wrist and the median nerve at the elbow. The anode and cathode will be approximately 3 cm apart and 1 cm in diameter. We will examine F-waves in first dorsal interosseous, flexor and extensor carpis radialis muscles.

Phase 2

Aim 2a. Enhance recovery of motor function by using non-invasive repetitive transcranial magnetic stimulation (rTMS)

To accomplish this aim we propose to complete two main experiments. First we will use rTMS to test the hypothesis that *rTMS induced cortical plasticity during movement will enhance voluntary output in hand muscles (as measures by electromyography and Jebsen Taylor Test) after spinal cord injury (Aim 2a)*. Second, we will combine precision grip and wrist training with rTMS to test the hypothesis that *precision grip training outcomes will be enhanced by rTMS induced cortical plasticity (aim 2b)*.

Experiment 1 (Aim 2a)

Participants will be randomly assigned to three groups: (1) rTMS, (2) Sham rTMS and (3) sham rTMS over control brain area. Randomization will be performed by lottery (i.e. Drawing from an envelope a piece of paper indicating the intervention). In the first two groups, rTMS stimulation will be targeting finger and wrist muscles during precision grip and write voluntary contractions. In the last group, rTMS will be applied over the dorsolateral prefrontal cortex (DLPFC) or at the leg presentation of the primary motor cortex, or at other related control area as needed. Each subject will be asked to participate in all sessions separated by a washout period of approximately one week. During testing, subjects will be seated in an armchair with both arms flexed at the elbow by 90 degrees. In each group we will use the same apparatus described in Aim1. At the start of the experiment subjects will perform 3 brief MVCs (3-5s) into index finger abduction and wrists flexion and extension, separated by 30 seconds. The maximal forces will be used to set targets for subsequent submaximal contractions.

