rTMS protocol- rTMS will be applied by a magnetic stimulator through a figure of eight coil with the same coil position as in Aim1. rTMS will consist of a total of 1200 pulses at an intensity of 80% of the AMT applied during a precision grip. At each time three targets will be presented on a computer screen. Each target will indicate a GO signal to complete a precision grip. During each precision grip 5 pulses at 5Hz will be applied. In total, 8 blocks of 10 trains of 15 pulses at 5Hz separated by inter train interval of 10s will be applied (1200 pulses). Each block will be separated by 30s of rest. The periods of stimulation will last approximately 24 minutes.

Measurements before and after rTMS protocol- We will examine: (a) MEPs, SICI, and F-waves (see procedures in AIM1), and (b) EMG and force output. Before rTMS, to examine EMG and force output individuals will receive visual feedback on a computer screen corresponding to 10% of MVC during a precision grip. The target will be presented for 1 second and then it will disappear at intervals of 5-6 seconds. Subjects will be instructed to reach the target as accurately as possible without making any corrections. Three sets of 20 repetitions will be tested. Signals will be acquired and the mean of force displacement plus 1 standard deviation (SD) will be calculated. After rTMS, subjects will not be told whether the visual feedback is derived from their actual or from their previous performance. Then, the visual feedback presented in the computer screen will correspond to mean forces +1SD values exerted prior rTMS.

The Jebsen Taylor Hand Function Test

The JHFT was developed to provide a standardized and objective evaluation of several major aspects of hand function using simulated activities of daily living.

(Jebsen et al. 1969)

The Jebsen Taylor Hand Function Test is a standardized test with high intra-tester ($r = 0.85$; $p > 0.05$) and inter-tester reliability (intraclass correlation coefficient ranging from 0.82 to 1.00). It is designed for adults with neurological or musculo-skeletal conditions involving hand disabilities. The test items include a range of fine motor, weighted and non-weighted hand function activities: (i) writing (copying) a

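### The Aim 2a ANOVA makes no stated use of the pre-rTMS values, and Aim 2b does not say whether its session-1 level is the untreated value

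*Combined protocol and SAP*

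**What the plan says.** **Aim 2a.** Section G specifies a repeated-measures ANOVA with Tukey post hoc tests for "the effect of TIME (0,10, 30, 60 min after a single rTMS session" and for STIMULATION. Experiment 1 does collect baseline data: "Measurements before and after rTMS protocol- We will examine: (a) MEPs, SICI, and F-waves", together with EMG and force output. The only stated use of any pre-rTMS value is to set the visual feedback shown in the force task afterwards. Section G mentions no baseline level, covariate, change score or normalisation.

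The design is described in two ways. Experiment 1 says "Participants will be randomly assigned to three groups", and then "Each subject will be asked to participate in all sessions separated by a washout period of approximately one week".

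**Aim 2b.** The plan for long-term effects says "Physiological and behavioral measurements will be acquired before and after sessions 1,5, and 10". Section G lists "TIME (sessions number 1,5,10 and follow up 1,2, and 3 months", which is one level per session, without saying whether the before or the after value enters.

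**Outcome scale.** The Methodology states "The primary outcome measures of this study are muscle responses to stimulation with magnetic pulses using TMS", along with responses to peripheral nerve stimulation. For MEP testing, "TMS intensity will be adjusted to produce an MEP of 50% of the maximal MEP on each muscle tested". Whether MEPs are analysed raw or relative to the maximum is not stated.

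**The concern.** Aim 2a asks whether rTMS enhances motor output. With post-stimulation levels only, TIME describes how responses evolve over the hour after stimulation. A STIMULATION x TIME test, if run, asks whether that course differs between conditions. A shift that appears at once and persists adds nothing to either test and shows only in the STIMULATION main effect, which is then unadjusted for where each subject started. Data that could sharpen that comparison are collected but given no analytic role. The choice between a covariate, a change score and no baseline can be made after the data are seen.

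In Aim 2b the meaning of the GROUP test depends on an undefined level. If session 1 is the value before any stimulation, GROUP averages in a level where no effect can exist, and part of the effect sits in GROUP x TIME. If it is the value after session 1, the model has no untreated reference.

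**Working it through.** The documents give no alpha, power, effect size, SD or correlation, and no figure of theirs is disputed. All inputs below are assumptions: unit variances, two-sided alpha 0.05, and 80% power for the post-only test (2.802 = 1.960 + 0.842).

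**1. What post-only levels can show.** Two parallel groups, 30 per arm, constant shift of 0.5 SD at all post times, correlation 0.5. In 4,000 simulated trials the post-only STIMULATION x TIME test rejected in 0.047, which is alpha. With a pre-rTMS level added it rejected in 0.46 (0.34 to 0.88 for correlations 0.3 to 0.8, by noncentral F).

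**2. Aim 2a, one condition per subject.** Let a be the pre-post and b the post-post correlation. The mean of four post values has variance m = (1 + 3b)/4. The adjusted-to-unadjusted variance ratio is 1 - a²/m, and power becomes Phi(2.802/√ratio - 1.960). With b = 0.7, m = 0.775:

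| a | ratio | power |
|---|---|---|
| 0.1 | 1 - 0.01/0.775 = 0.99 | 0.81 |
| 0.3 | 1 - 0.09/0.775 = 0.88 | 0.85 |
| 0.5 | 1 - 0.25/0.775 = 0.68 | 0.93 |
| 0.7 | 1 - 0.49/0.775 = 0.37 | above 0.99 |

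With a = b the ratio is 0.81 at 0.3 and 0.60 at 0.5. Estimating the covariate slope multiplies the variance by 1 + 1/(2n - 4): 1.018, 1.038 and 1.063 at n = 30, 15 and 10 per arm. So there is no gain when a is near 0.1 or below. A change score has ratio (m + 1 - 2a)/m, which exceeds 1 whenever a < 0.5 (1.52 at a = 0.3, b = 0.7).

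**3. Aim 2a, all conditions per subject.** Subject differences already cancel, so the gain depends on the within-subject, session-to-session pre-post correlation r. For two conditions the large-sample ratio is 1 - 4r²/(1 + 3r): 1.00, 0.81 and 0.60 at r = 0, 0.3 and 0.5. Simulation with 30 subjects and a period term, with the baseline centred on the subject's mean, gives about 1.05, 0.83 and 0.63. With the raw session baseline and only a random subject intercept, the ratios are 1.18-2.27 at r = 0 and 0.88-1.18 at r = 0.3 (subject variance share 0.3 to 0.7), falling to 0.67-0.86 at r = 0.5.

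**4. Aim 2b, if session 1 is untreated.** Assume compound symmetry with correlation rho and an equal effect at the five later levels. Adding the null level multiplies the mean difference by 5/6 and changes the variance from (1 + 4·rho)/5 to (1 + 5·rho)/6. GROUP power falls from 80% to 0.670, 0.658 and 0.652 at rho = 0.3, 0.5 and 0.7. With the variance unchanged it is Phi(2.802 × 5/6 - 1.960) = 0.646.

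For GROUP x TIME the noncentrality is n(5/12)d²/(1 - rho), where d² = 2.802² × 2[(1 + 4·rho)/5]/n. This reduces to 6.54[(1 + 4·rho)/5]/(1 - rho) = 4.11, 7.85, 16.57 and 27.48 at rho = 0.3, 0.5, 0.7 and 0.8. On 5 and 290 degrees of freedom (30 per arm) the power is about 0.29, 0.55, 0.90 and 0.99.

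**The case against.** **Validity.** A reader might infer that the sham comparison fails without a baseline, or that no baseline is taken. Neither is supported. Randomisation makes the contrast of post values valid, and Experiment 1 does take pre-rTMS measurements.

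**Zero minutes as baseline.** This does not fit the wording, which places all four times after the session. Even if it did, the role of the pre-rTMS values would remain unstated.

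**The gain may be nil.** This stands in part. If MEPs are expressed relative to the maximal MEP, setting the intensity to half of maximum leaves little baseline variation to use. In a crossover with low r there is nothing to gain. That limits the size of the point. It does not remove it for SICI, F-waves, EMG and force, and adjustment costs little.

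**Aim 2b.** A reader might take the fall to 65-67% as the power of the plan, or an untreated first level as an error. Neither follows. Baseline as the first TIME level is a conventional layout. GROUP x TIME, which section G does not name but such a model normally includes, would exceed 80% power at correlation 0.7 or above. At 0.3 and 0.5 it does worse than GROUP. The difficulty is that neither the level nor the deciding test is defined. The equal effect from session 5 to three months is also only an assumption.

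**Raw baseline in a crossover.** An outright ban would go too far: it loses precision at low r and gains at 0.5.

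**Conclusion.** The point holds as a gap in specification with a possible loss of precision; it is not a threat to the validity of the comparison with sham. Section G gives the Aim 2a pre-rTMS values no analytic use, and its TIME terms cannot show a pre-to-post change. In Aim 2b the text does not settle whether session 1 is the untreated reference, and the test that carries the treatment effect changes with the answer.

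The benefit of adjustment runs from none to a large reduction in variance, depending on correlations that the documents do not give and on an Aim 2a design that they describe in two ways. The change should be made because it is cheap and uses data already collected. Confidence in the size is moderate at most.

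**What to change.** 1. State whether each Aim 2a subject receives one condition or all.
2. Aim 2a, one condition: model the post values with the pre-rTMS value as covariate, plus condition, time and condition x time. Prefer this to a change score.
3. Aim 2a, all conditions: include the session's pre-rTMS value together with fixed subject effects, or centred on the subject's mean with a random subject intercept; add period. Note that a raw session baseline with only a random intercept can lose precision when the within-subject pre-post correlation is about 0.3 or less.
4. Aim 2b: state whether each session level is the before or the after value. Use the before-session-1 value as a baseline covariate and model the later assessments with group, time and group x time. Include an SCI/control term, because Experiment 2 randomises both populations.
5. In both aims, name the baseline-adjusted condition contrast as the deciding test for outcomes with a pre-stimulation measurement, and state whether MEPs are analysed raw or relative to the maximum.

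The cost is SAP wording and one degree of freedom: about 2-6% in variance at 30 to 10 per arm, or about 2-5% in a 30-subject crossover, if the baseline carries no information. No new data are needed for MEPs, SICI, F-waves, EMG and force. Whether the Jebsen Taylor test is done before rTMS in Aim 2a must be confirmed, since the list of before-and-after measurements does not name it.
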